6. STUDY PROCEDURES AND ASSESSMENTS

6.1. Day -1 – Pre-screening

Interested potential participants who contact the research site will undergo a brief pre-screening questionnaire via phone to determine initial eligibility. Potential participants will be assigned a screening number in order to de-identify the information on the form. The pre-screening form can be found in Appendix 11.2.1.

6.2. Day 0 - Informed Consent and Screening Visit

6.2.1. Informed Consent

Upon arrival to the study site, research staff will provide potential participants with a written informed consent form (ICF) that has received approval by an institutional review board (IRB) or Ethics Committee. The ICF will be written and administered in compliance with Good Clinical Practice (GCP) and comply with all elements required by FDA 21 CFR 50.25, International Conference on Harmonization (ICH), and state and local regulations. Research staff will answer any questions the potential participant has regarding the form. Written consent from the participant must be obtained prior to conducting any other research activities. A copy of the signed ICF will be offered to each participant.

6.2.2. Screening

After obtaining informed consent, research staff will assess eligibility to participate in the study using the screening form provided in Appendix 11.2.2. Participants who qualify will be assigned a subject number. In the event the potential subject has not had a measurement to determine adequate blood flow in the past three months, the PI or research staff will assess blood flow via a handheld vascular Doppler device. Subjects must meet the Doppler criteria mentioned in section 5.1 of this protocol to be randomized

6.3. Day 1 – Initial Visit

6.3.1. Demographic and Baseline Data Collection

The PI or research staff will collect the following demographic data and medical information: age, gender, race, height, weight, medical diagnoses, wound location, wound type, duration of wound, and prior treatments. These data will be recorded on the Initial Visit Case Report Form (CRF), provided in Appendix 11.3.1.

6.3.2. Photograph of Wound and Wound Size Measurement

Measurement of wound size will occur via software provided with an acceptable wound camera, to be provided by Medline. The PI will take a photograph of the wound with the camera and upload the file to a computer with appropriate software. The software will automatically calculate the wound size; this will serve as the wound size data point for the Initial Visit. Wound size, in cm^2 will be recorded on the Wound Photo CRF; a copy of the CRF is provided in Appendix 11.3.2.

6.3.3. Pain Assessment

Participants will verbally rate their perceived pain level twice during the visit. A “current” pain level will be captured by asking the participant his/her current pain during the visit; this measurement will be obtained at the beginning of the visit. If debridement is to be performed during the visit, the “current” pain evaluation will occur prior to debridement. Additionally, a pain level during dressing changes will also be acquired. Participants will use a 0-10 Verbal Numeric Pain Rating scale, with 0 corresponding to minimal pain and 10 indicating the worst pain imaginable. The value will be recorded on the Wound Photo CRF.

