1.2. Schedule of Activities (SOA)

REQUIRED ASSESSMENTS	PRE-SCREENING Day -1	SCREENING VISIT Day 0 (May be combined with Initial Visit, Day 1)	INITIAL VISIT Day 1	DRESSING CHANGE VISITS Twice weekly (Every 3 days ± 1 day)	WOUND ASSESSMENT VISITS Once per week Every 7 days ± 2 days (May be combined with Dressing Change Visit)	FINAL VISIT 12 weeks from Initial Visit ³
Pre-Screening Questionnaire ¹	X					
Informed Consent		X				
Screening Form to assess eligibility		X				
Decision on eligibility		X				
Demographics			X			
Wound History			X			
Wound Photograph			X		X	X
Bates-Jensen Wound Assessment			X		X	X
Application of Puracol® Ultra			X	X	X ²	
Pain Assessment for dressing change			X		X	X
Secondary Dressing Notation			X	X	X ²	
Adverse Event Assessment		X	X	X	X	X

1: For participants contacting the research facility, 2: If combined with Dressing change visit, 3: Final visit may occur earlier in the event the participant's wound has completely healed before 12 weeks

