2.2. Investigational Product

Puracol® Ultra Powder collagen wound dressing is a powder-like fibrillar collagen microsponge composed of Type I porcine dermis collagen. The dressing is a currently marketed, cleared device in the United States, indicated for the management of full and partial thickness wounds, including: pressure ulcers, diabetic ulcers caused by mixed vascular origin, venous ulcers, and several other wound types. Appendix 11.1.1 provides the label and instructions for use (IFU) for the device.

As Puracol® Ultra comes in powder form, a secondary dressing applied over the wound is necessary. An appropriate sized dressing from the Optifoam® Gentle silicone border series by Medline Industries Inc., will be applied. Information pertaining to these dressings is provided in Appendix 11.1.2. Furthermore, given that the standard of care for patients with venous ulcers entails

Fibrillar dressing for treating chronic, stalled wounds

MED-2018-DIV71-008

23 August 2018

V 1.0

CONFIDENTIAL

application of a compression dressing, patients with these types of wounds will also receive CoFlex® TLC Two-Layer Compression System dressing; this dressing is currently marketed for the management of venous ulcers. More information regarding the CoFlex® TLC Two-Layer Compression System dressing is available in Appendix 11.1.3.

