6.3.5. Dressing Application

Following the wound assessment, the Investigator or other clinician on the research staff will cleanse the wound using a wound cleansing solution and apply the Puracol® Ultra Powder

dressing to the wound. A notation as to the type of secondary dressing applied will be noted on the Dressing Log CRF (see Appendix 11.3.4).

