8.3.3. Pain Scale Analysis

Descriptive measures of central tendency and variability will be provided for pain rating at the Initial Visit and the Final Visit. A 95% confidence interval for mean change in pain will also be calculated, assuming normality of the data. For exploratory purposes, paired samples t-test will be conducted on wound size at the Initial Visit vs. Final Visit to identify any significant differences in wound size over the course of the study; if the data are not normally distributed, a non-parametric test will be used. Though these data are technically on an ordinal scale, the ten-point scale allows for the mean value to be more informative, and for the potential of conducting parametric tests. Finally, change in pain over time may also be modeled similarly to change in wound size.

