11.1.2. Optifoam® Gentle Silicone Border Dressings

Optifoam Gentle silicone border dressings are currently marketed dressings indicated for the management of partial and shallow full-thickness wounds. The dressings aid in providing a moist wound environment and the absorption of exudate, which aids in wound healing. The silicone adhesive is often less traumatic and painful upon removal compared to acrylic based adhesives. The dressings that will be used in this study are available in four sizes: 1/6" x 2", 3" x 3", 4" x 4", and 6" x 6".

Fibrillar dressing for treating chronic, stalled wounds

MED-2018-DIV71-008

23 August 2018

V 1.0

CONFIDENTIAL

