11.3. Case Report Forms

11.3.1. Initial Visit Case Report Form

Initial Visit Case Report Form		
MED-2018-DIV71-008: A case series evaluating a fibrillar collagen powder dressing to treat chronic, stalled lower-extremity wounds		
Demographic Data		
Subject Number:	Age:	Gender: Male  Female 
Height (in):	Weight (lbs):	
Race (may select more than one): Black  White  Asian  Hispanic  Other 		
Relevant Medical Diagnoses and Current Medications:		
Wound History		
Wound Type:		
Wound Location:		
Duration of wound (in months):		
Prior treatments and duration:		
Has mechanical debridement been performed?		Yes  No 
Form Completed by:		Date:

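### The Initial-to-Final change in dressing-change pain may include an effect of switching to the study dressing, of unknown size and possibly zero, which the plan does not separate from healing

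*Combined protocol and SAP*

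**What the plan says.** Section 3 lists two pain components under the secondary endpoint, general pain and pain at dressing change, and justifies pain as a marker of healing. Section 6.3.3 takes a current rating at the start of the visit and adds that "a pain level during dressing changes will also be acquired", on a 0–10 verbal scale. The Schedule of Activities (1.2) places "Pain Assessment for dressing change" at the Initial Visit, the weekly Wound Assessment Visits and the Final Visit.

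On the dressing itself, section 6.3.5 says of the Initial Visit: "Following the wound assessment, the Investigator or other clinician on the research staff will cleanse the wound" and then apply the study powder. Section 2.2 specifies the cover: "An appropriate sized dressing from the Optifoam® Gentle silicone border series by Medline Industries Inc., will be applied". For venous ulcers it adds that "patients with these types of wounds will also receive CoFlex® TLC Two-Layer Compression System dressing". Appendix 11.1.2 describes the cover: "The silicone adhesive is often less traumatic and painful upon removal compared to acrylic based adhesives".

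Section 8.3.3 gives descriptive measures for "pain rating at the Initial Visit and the Final Visit" and a 95% confidence interval for mean change in pain. It does not distinguish the two ratings and does not mention the change of dressing.

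**The concern.** A change score is interpretable when the same thing is measured at both ends. Here the dressing handled at the first rating is probably not the kind handled at the last. The protocol itself gives a reason why the later kind might hurt less to remove, at least for participants who came in with acrylic adhesives. In a single-arm study nothing subtracts that effect. A fall in dressing-change pain could then be read as healing when some of it came from the switch of cover. What is at stake is the interpretation of one of the two pain components of a secondary endpoint.

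**Working it through.** The plan states no figure on this point, and section 8.1 says that no power analysis was done, so there is nothing to reproduce. The check has two parts.

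**1. Which dressing does each rating concern?**

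- Initial Visit: the study dressing is first applied after the wound assessment (6.3.5), so any dressing removed that day predates the study.
- Weekly visits: section 6.5 repeats the assessments of 6.3.2 to 6.3.4 and changes the dressing if one is due. The dressing removed is then the study cover (2.2), with compression for venous ulcers.
- Final Visit: section 6.6 repeats 6.3.1 to 6.3.4 but not the application step in 6.3.5, and the Schedule shows no application at that visit. The dressing in place beforehand is the study cover.
- Rated step: section 6.3.3 does not say whether the rating covers removal, cleansing or application. That the Initial Visit rating concerns the earlier dressing is an inference from the order of events.
- Record of the earlier dressing: the Initial Visit CRF (11.3.1) has a free-text line, "Prior treatments and duration", but no field for the dressing or adhesive in place that day. The Wound Photo CRF (11.3.2) holds the two pain scores, and the Dressing Log (11.3.4) records what is applied, not what is removed.

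The change therefore compares two different dressings, and the forms do not reliably show how they differed.

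**2. How much could it matter?**

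Mean shift from the switch = (share of participants whose earlier dressing hurt more to remove) × (mean extra pain points in that group). The documents give neither factor. Examples: 0 × any value = 0; 0.5 × 1 point = 0.5; 0.5 × 2 points = 1.0.

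Assumptions not in the documents: SD of change 2 to 3 points, mean shift 0.25 to 2 points, no healing effect, and a two-sided 5% paired t-test on pain. From the documents: n = 20. Because section 8.2 restricts the analysis to evaluable participants, n = 15 is shown as an assumed smaller set.

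Chance of significance = P(|T| > t(0.975, n−1)), where T is noncentral t with n−1 degrees of freedom and noncentrality (shift/SD) × √n. For a shift of 1, SD 2 and n = 20, the noncentrality is 0.5 × 4.472 = 2.24 and the chance is 0.565.

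| n | SD | shift 0.25 | shift 0.5 | shift 1 | shift 2 |
|---|---|---|---|---|---|
| 20 | 2 | 0.083 | 0.186 | 0.565 | 0.989 |
| 20 | 2.5 | 0.071 | 0.136 | 0.397 | 0.924 |
| 20 | 3 | 0.064 | 0.109 | 0.294 | 0.807 |
| 15 | 2 | 0.074 | 0.147 | 0.438 | 0.949 |
| 15 | 2.5 | 0.065 | 0.112 | 0.303 | 0.821 |
| 15 | 3 | 0.060 | 0.092 | 0.225 | 0.671 |

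At zero shift the chance is the nominal 5%.

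The planned confidence interval has half-width t(0.975, n−1) × SD/√n. At n = 20 this is 0.94 (SD 2), 1.17 (SD 2.5) and 1.40 (SD 3). With SD 2, a one-point shift alone would centre the interval on 1.0, running from 0.06 to 1.94.

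**The case against.** A reader might infer that the endpoint is biased toward benefit. The documents do not support that. The statement in 11.1.2 says only often, and compares only with acrylic adhesives. Nothing says that participants arrived with acrylic dressings, or with adhesive ones at all. Section 2.1 names silver sulfadiazine, calcium alginate and hydrocolloid as earlier treatments without describing their adhesive, and some participants may already have worn silicone. Compression adds handling at on-study changes for venous ulcers, and its earlier use is unknown, so the direction is not settled for them either. All of this stands.

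The illustration also deserves little weight. It spans about 6% to 99% at n = 20 according to what is assumed. It further presumes a paired test on pain, whereas the t-test sentence in 8.3.3 literally names wound size and needs correcting in its own right. The planned interval for mean change in pain is open to the same shift.

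The importance is limited: this is an uncontrolled series of 20 with testing labelled exploratory, and current pain is rated at the start of the visit. Finally, making week 1 the sole baseline would replace a pre-treatment value with an on-treatment one and discard any early benefit. That is a good reason to use week 1 only as a sensitivity analysis.

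What survives is that the dressing very likely differs between the two ratings, and no section addresses it.

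**Conclusion.** The point holds as a limit on interpretation. The Initial-to-Final change in dressing-change pain may mix a switch of dressing with healing, and the plan has no control arm or analysis to separate them. The effect is of unknown size, and it is zero if earlier dressings were no more painful to remove. The conclusion rests on the inference, from visit order, that the Initial Visit rating concerns the earlier dressing. The significance figures show only that a shift of a point or more could matter with 20 participants; they do not show that such a shift exists. This is a minor point, worth settling because the remedy is cheap.

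**What to change.** In section 8.3.3:

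- Analyse current pain and dressing-change pain separately. Leave Initial-to-Final change as it is for current pain.
- For dressing-change pain, keep the Initial-to-Final change, but label the Initial Visit value as pain with the pre-study dressing.
- Add a sensitivity analysis of change from the first weekly Wound Assessment Visit at which a study dressing is removed to the Final Visit. The condition is needed because section 6.5 makes the change at that visit depend on whether one is due.
- State that a fall in dressing-change pain will be attributed to healing only if the sensitivity analysis agrees.

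The cost is a few lines of text and a little extra analysis of ratings already scheduled. The week-1 comparison does not count any first-week benefit, and a participant whose wound has healed by that visit contributes no later rating to it.

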1. PROTOCOL SUMMARY

1.1. Synopsis

Title: A prospective case series evaluating a fibrillar collagen powder dressing to treat chronic, stalled lower-extremity wounds

Study Description: Chronic wounds are a source of significant morbidity and escalating healthcare costs. The wound care professional has a myriad of modern wound dressings to choose from when treating a wound, each of which has benefits and drawbacks. An understanding of how a given dressing performs in healing a particular wound is crucial in order to determine a clinical mapping of wound dressings to wound types; such a categorization would lead to more efficient clinical decision making and better patient outcomes. This case series will evaluate the ability of a fibrillar collagen powder to improve healing of chronic, stalled, lower-extremity wounds.

Objectives: Evaluate the ability of a fibrillar collagen powder dressing to treat chronic, stalled, lower-extremity wounds

Endpoints: **Primary:** Change in wound size over twelve week period
Secondary: 1) Change in Bates-Jensen Wound Assessment Tool score, 2) Change in reported pain level.

Study Population: Twenty adult patients with chronic lower-extremity wounds (i.e. below the knee) of greater than four weeks that have failed to respond to at least one advanced wound dressing treatment. Specific wound types include: pressure ulcers, diabetic ulcers, and venous leg ulcers.

Phase: Post-Market

Description of Sites/Facilities Outpatient podiatry clinics in the United States
Enrolling Participants:

Description of Study Intervention: Patients who meet the inclusion criteria will be provided with fibrillar collagen powder dressing (Puracol® Ultra Powder by Medline Industries, Inc.). The powder dressing will be used in

accordance with its label. After cleansing the wound by the clinical site staff, the powder is placed directly on the wound, and then the wound will be covered with an appropriate moisture retentive secondary dressing. Patients will visit the clinic twice a week to have the powder re-applied. Wound evaluations will take place once a week at the outpatient clinic, with the intervention lasting up to twelve weeks. Concurrent standard of care, such as compression for venous ulcers, will be provided.

Study Duration: Total time for study completion to allow accrual of all subjects, and appropriate treatment as per the protocol, will be approximately 12-18 months

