6.5. Wound Assessment Visit

One of the dressing change visits will serve as the wound assessment visit as well. Participants will come to the clinic every 7 days \pm 2 days so the PI can assess the wound. The assessments conducted at this visit will be identical to those described in Sections 6.3.2 to 6.3.4. Additionally, if the participant is due for a dressing change, one will occur at this visit as well. All events will be documented via the Wound Photograph, BWAT, and Dressing Log CRFs.

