6.6. Final Visit

The Final Visit will take place 12 weeks after participant enrollment; in the event the wound completely heals before 12 weeks have passed, the visit where the PI notes complete wound healing will serve as the Final Visit. Data collection will follow the same procedures defined in Sections 6.3.1 to 6.3.4.

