11.3.2. Wound Photo Case Report Form

Wound Photo Case Report Form

MED-2018-DIV71-008: A case series evaluating a fibrillar collagen powder dressing to treat chronic, stalled lower-extremity wounds

Place photograph of the wound below:

Subject Number: _____ **Date:** _____ **Wound Assessment Number:** _____

Wound Size: _____ cm² (enter value obtained from camera software platform)

Current Pain Rating: _____ **Dressing Change Pain Rating:** _____

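### The 0–10 pain scale anchors 0 at minimal pain, so no pain and minimal pain have no distinct codes and the pain-change endpoint can be off by about one point per affected participant, in either direction

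*Combined protocol and SAP*

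**What the plan says.** Section 6.3.3 (Pain Assessment) asks for two ratings at the Initial Visit: "Participants will verbally rate their perceived pain level twice during the visit". One is current pain and the other is pain at dressing change. Both use a 0–10 verbal numeric scale "with 0 corresponding to minimal pain and 10 indicating the worst pain imaginable".

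The scale carries forward unchanged. For the weekly visits, section 6.5 states: "The assessments conducted at this visit will be identical to those described in Sections 6.3.2 to 6.3.4". For the Final Visit, section 6.6 states: "Data collection will follow the same procedures defined in Sections 6.3.1 to 6.3.4".

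The ratings go on the Wound Photo CRF (11.3.2), which has one blank for current pain and one labelled "Dressing Change Pain Rating". Neither blank carries anchors, an option for none, or a coding rule.

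The Synopsis (1.1) lists "Change in reported pain level" as a secondary endpoint, and section 3 splits it into general pain and pain at dressing change. Section 8.3.3 summarises the Initial and Final Visit ratings and adds: "A 95% confidence interval for mean change in pain will also be calculated, assuming normality of the data". It justifies using means on the ground that "the ten-point scale allows for the mean value to be more informative".

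**The concern.** A numeric pain scale needs a bottom value with a single meaning. Here the lowest value is assigned to a state in which some pain is present, and nothing lies below it. A participant with no pain has to share that value, or the rater has to depart from the stated anchor.

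This matters because section 3 justifies the pain endpoint as a marker of healing and wound status, so the low end of the scale is where a good outcome would appear. No entry criterion in 5.1 or 5.2 requires pain at baseline, so low ratings are possible at either visit. The analysis is a mean change between two visits, so a one-step ambiguity at either visit passes directly into the estimate. Section 8.1 also allows the data to inform the power calculation of a later trial.

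**Working it through.** The plan gives no figure to reproduce. The sample of 20 was not derived from a power calculation (8.1), and no pain distribution, standard deviation or expected change is stated. The check is therefore a comparison of the sections, followed by arithmetic on a simple comparator.

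**1. Is a value for no pain given anywhere?** Pain is defined in 6.3.3, repeated by reference in 6.5 and 6.6, recorded in 11.3.2 and analysed in 8.3.3. Only 6.3.3 states anchors. None of the others supplies a no-pain code or overrides the anchor.

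**2. What does the anchor do to a recorded change?** Take as comparator a scale with none = 0 and minimal = 1, all higher scores being the same on both scales. As written, none = 0 and minimal = 0. Define reduction = Initial − Final, and error = reduction as written − reduction on the comparator.

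| Initial → Final | Comparator | As written | Error |
|---|---|---|---|
| minimal → none | 1 − 0 = 1 | 0 − 0 = 0 | −1 |
| 5 → minimal | 5 − 1 = 4 | 5 − 0 = 5 | +1 |
| 5 → none | 5 − 0 = 5 | 5 − 0 = 5 | 0 |
| minimal → minimal | 1 − 1 = 0 | 0 − 0 = 0 | 0 |
| none → minimal | 0 − 1 = −1 | 0 − 0 = 0 | +1 |

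The score of 5 is only an example of a value above the floor. In general, a participant's error is +1 if pain is minimal at the Final Visit only, −1 if it is minimal at the Initial Visit only, and 0 otherwise.

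**3. Effect on the mean.** With n evaluable participants, of whom k have an error of the same sign and the rest have none, the mean change shifts by k/n. For n = 20:

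- k = 1: 1/20 = 0.05 points
- k = 5: 5/20 = 0.25 points
- k = 10: 10/20 = 0.50 points
- k = 20: 20/20 = 1.00 point, the ceiling

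Errors of opposite sign cancel in the mean. The evaluable set in 8.2 may be smaller than 20, and k would then be divided by that smaller number.

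**4. If the anchor is not followed uniformly.** A participant who treats 0 as none and 1 as minimal behaves as on the comparator, with no error. The data would then mix two conventions, and the CRF gives no means of telling which one lies behind a recorded 0.

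**The case against.** Several points on the other side are sound.

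- **A pain-free participant can still be rated.** A reader might infer that such a participant has no value to give. That goes too far: 0 is available as the lowest score. What is missing is a value distinct from minimal pain.
- **The bias is not simply attenuation.** A reader might infer that improvement is always understated. The table shows this only for a participant who starts at minimal pain and ends with none. A fall from a higher score to minimal pain is overstated, and a fall from a higher score to none is recorded correctly.
- **The share of final ratings at the floor does not measure the error.** Participants who reach no pain from above the floor contribute nothing, so that share cannot be multiplied by one point to give the shift in the mean. The relevant count is the k defined above.
- **The documents do not show what participants hear.** Section 6.3.3 describes the scale, but there is no participant script. The wording may be a slip for no pain that staff would correct unprompted. Nothing in the documents shows this, and if it is a slip, the text still needs correcting.
- **Little depends on it.** Pain is secondary, testing is exploratory, there is no success threshold, and 20 was not a powered number. This limits the severity but does not remove the ambiguity.

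Calling a 0–10 scale ten-point in 8.3.3, when it has 11 integer values, is a clerical matter. The range is clear from 6.3.3, and no result depends on the label.

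**Conclusion.** The point holds as a minor measurement defect. As defined in 6.3.3, the scale has no separate codes for no pain and minimal pain, and no other section repairs this. The consequence is a possible distortion of about one point per affected participant in the secondary pain-change endpoint, upward or downward, or else a 0 whose meaning varies between participants. For 20 evaluable participants the mean change shifts by k/20 points.

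That size rests on three assumptions: all 20 participants are evaluable, minimal pain would score 1 on a scale with a no-pain anchor, and the k affected participants err in the same direction. The documents do not allow k to be estimated, so the values shown illustrate a range and do not predict a bias. Wound size, BWAT score and the sample size are untouched.

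**What to change.** Before first enrolment, change the lower anchor in 6.3.3 so that 0 corresponds to no pain, leaving the upper anchor as it is. Print both anchors beside the two pain fields on the Wound Photo CRF (11.3.2), so that raters use the same wording at every visit. Sections 6.5 and 6.6 refer back to 6.3.3 and need no edit. The label in 8.3.3 can be changed to 11-point in the same revision as a tidy-up.

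The cost is a few words in the protocol and on one form, with no added procedure, visit or data field. The change should come before data collection, because ratings already taken under the ambiguous anchor cannot be recoded afterwards.
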